APPENDIX 2 AIDS-DEFINING DIAGNOSES

I. PARASITIC INFECTIONS

Pneumocystis carinii (PC)

1011 PC pneumonia histologically proven.

1012 PC pneumonia, clinical diagnosis by the following specifications and confirmed HIV infection:

A history of dyspnea on exertion or non-productive cough of recent onset (within the past 3 months).

AND

Chest X-ray evidence of diffuse bilateral interstitial or gallium scan evidence of diffuse bilateral pulmonary disease;

AND

Arterial blood gas analysis showing an arterial pO₂ of < 70 mmHg or a low respiratory diffusing capacity (< 80% of predicted values) or an increase in the alveolar-arterial oxygen tension gradient;

AND

Successful response to appropriate therapy and no evidence of pneumonias of other etiologies.

1013 Pneumocystis carinii, histologically proven, at a site other than lungs.

Toxoplasmosis (in patients > 1 month old)

1021 Toxoplasmosis, clinical diagnosis (of brain only) by the following specifications and confirmed HIV infection:

Recent onset of a neurologic disease consistent with toxoplasmosis;

AND

Brain imaging evidence of a mass lesion (on computed tomography, nuclear magnetic resonance or radiography enhanced by injection of contrast medium);

AND

Serum antibody to toxoplasmosis and successful response to therapy for toxoplasmosis.

1022 Toxoplasmosis, of brain or internal organs other than liver, spleen or lymph nodes. Proven by microscopy.

Isosporiasis

1031 Isosporiasis causing chronic diarrhea of > 1 month. Proven by microscopy.

Cryptosporidiosis

1041 Cryptosporidiosis causing chronic diarrhea of > 1 month. Proven by microscopy.

II. FUNGAL INFECTIONS

Candidiasis

2011 Candidiasis, Esophageal, definitive diagnosis by the following specifications:

Gross inspection by endoscopy or autopsy or by microscopy (histology or cytology) on a specimen obtained directly from the tissues affected (including scrapings from the mucosal surface), not from a culture.

2012 Candidiasis, Esophageal, presumptive diagnosis by the following specifications and confirmed HIV infection:

Recent onset of retrosternal pain on swallowing:

AND

Oral candidiasis diagnosed by the gross appearance of white patches or plaques on an erythematous base OR by the microscopic appearance of fungal mycelial filaments in an uncultured specimen scraped from the oral mucosa;

AND

Response to appropriate therapy.

2013 Candidiasis, Bronchial/Pulmonary, definitive diagnosis by the following specifications; Gross inspection by endoscopy or autopsy or by microscopy (histology or cytology) on a specimen obtained directly from the tissues affected (including scrapings from the mucosal surface), not from a culture.

Cryptococcosis

2022 Cryptococcosis, Extra-pulmonary, proven by microscopy (histology or cytology), culture or detection of antigen in a specimen obtained directly from the tissues affected or a fluid from those tissues.

Histoplasmosis

2031 Histoplasmosis, Disseminated (at a site other than or in addition to lungs or cervical or hilar lymph nodes), proven by microscopy (histology or cytology), culture or detection of antigen in a specimen obtained directly from the tissues affected or a fluid from those tissues.

Coccidioidomycosis

2041 Coccidioidomycosis, Disseminated (at a site other than or in addition to lungs or cervical or hilar lymph nodes), proven by microscopy (histology or cytology), culture or detection of antigen in a specimen obtained directly from the tissues affected or a fluid from those tissues.

2042 Coccidioidomycosis, clear reactivation of prior infection, proven by microscopy (histology or cytology), culture or detection of antigen in a specimen obtained directly from the tissues affected or a fluid from those tissues.

III. BACTERIAL INFECTIONS

Mycobacterium

3001 Mycobacterium (unidentified species). Presumptive diagnosis, by the following specifications and confirmed HIV infection.
Acid fast bacilli (AFB) positive stain of specimen obtained from endoscopic biopsy or from a normal sterile site other than lungs, skin or cervical or hilar lymph nodes. Species NOT identified by culture.

Mycobacterium tuberculosis

3011 Mycobacterium tuberculosis, Pulmonary, definitive diagnosis proven by culture, without evidence of upper respiratory infection symptoms of Mycobacterium tuberculosis that could account for the positive culture.

3012 Mycobacterium tuberculosis, definitive diagnosis proven by culture, of at least one extra pulmonary site regardless of concurrent pulmonary involvement.

3013 Mycobacterium tuberculosis, Disseminated, definitive diagnosis proven by culture.

Mycobacterium avium intracellulare

3022 MAI in Blood, proven by culture.

3023 MAI Colitis, proven by histology and culture. (This does not include MAI of the stool alone).

3024 MAI, Disseminated, at a site other than or in addition to lungs or cervical or hilar lymph nodes, proven by culture.

Mycobacterium Kansasii, Mycobacterium Scrofulaceum and Other Atypical Mycobacterium

3032 M. Kansasii, in Blood, proven by culture.

3033 M. Kansasii Colitis, proven by histology and culture. (NOT including positive M. Kansasii of stool alone).

3034 M. Kansasii, Disseminated, at a site other than or in addition to lungs, or cervical or hilar lymph nodes, proven by culture.

3035 M. Scrofulaceum or other Atypical Mycobacterium, proven by culture.

Salmonella

3041 Salmonella, recurrent Bacteremia (non-typhoid), proven by culture.

IV. VIRAL INFECTIONS

Cytomegalovirus

- 4011 CMV, Pneumonitis, pathologically or histologically confirmed. Serum antibody titer and culture alone is not sufficient for the diagnosis.
- 4012 CMV, Esophagitis, as diagnosed by histology, pathology or culture of an esophageal lesion. Serum antibody titer and culture of other than esophageal tissue is not sufficient for the diagnosis.
- 4013 CMV, Retinitis as evidenced by a characteristic appearance on serial ophthalmoscopic examinations (eg, discrete patches of retinal whitening with distinct borders, spreading in a centrifugal manner, following blood vessels, progressing over several months, frequently associated with retinal vasculitis, hemorrhage, and necrosis). Resolution of active disease leaves retinal scarring and atrophy with retinal pigment epithelial mottling.
- 4014 CMV, Colitis, as diagnosed by histology, pathology or culture of a colonic lesion. Serum antibody titer and culture of other than colonic tissue is not sufficient for the diagnosis.
- 4015 CMV, Encephalitis, as diagnosed by histology, pathology or culture of brain tissue or CSF. Serum antibody titer and culture of other than brain tissue or CSF is not sufficient for the diagnosis.

Herpes Simplex (in patients > 1 month old).

- 4021 HSV, Disseminated (but not encephalitis alone), proven by microscopy (histology or cytology), culture or detection of antigen in a specimen obtained directly from affected tissues.
- 4022 HSV, Esophagitis, as diagnosed by microscopy (histology or cytology), culture or detection of antigen in a biopsy specimen obtained directly from affected tissue. Serological measurement and culture from other than the affected tissue is not sufficient for the diagnosis.
- 4023 HSV, Bronchitis, as diagnosed by microscopy (histology or cytology), culture or detection of antigen in a biopsy specimen obtained directly from affected tissue. Serological measurement and culture from other than the affected tissue is not sufficient for the diagnosis.
- 4024 HSV, Pneumonitis, as diagnosed by microscopy (histology or cytology), culture or detection of antigen in a biopsy specimen obtained directly from affected tissue. Serological measurement and culture from other than the affected tissue is not sufficient for diagnosis.
- 4025 HSV, GI, other than mouth, throat, or peri-rectal, as diagnosed by microscopy (histology or cytology), culture or detection of antigen in a biopsy specimen obtained directly from affected tissue. Serological measurement and culture from other than the affected tissue is not sufficient for diagnosis.

4026 HSV, Mucocutaneous, ulcers persisting for ≥ 1 month despite appropriate therapy, as diagnosed by microscopy (histology or cytology), culture or detection of antigen in a biopsy specimen obtained directly from affected tissue. Serological measurement and culture from other than the affected tissue is not sufficient for the diagnosis.

Progressive Multifocal Leukoencephalopathy

4041 Progressive Multifocal Leukoencephalopathy, proven by microscopy.

VI. NEOPLASTIC DISEASES

Kaposi's Sarcoma

6011 Kaposi's sarcoma, Mucocutaneous, proven by microscopy.

6012 Kaposi's sarcoma. Mucocutaneous, presumptive diagnosis with characteristic gross appearance and confirmed HIV infection.

6013 Kaposi's sarcoma, Visceral.

6014 Kaposi's sarcoma, other than above.

Lymphoma of the Brain

6021 Primary Lymphoma of the brain at any age, proven by microscopy.

Non-Hodgkins Lymphoma

6031 Small Non-cleaved lymphoma (either Burkitt or non-Burkitt type).

6032 Immunoblastic sarcoma, equivalent to any of the following, although not necessarily all in combination: Immunoblastic lymphoma, large-cell lymphoma, diffuse histiocytic lymphoma.

Cervical Carcinoma

6041 Histologically proven invasive carcinoma of the cervix.

VII. OTHER CONDITIONS

HIV Dementia/Motor Defects

7011 HIV Dementia, clinical findings of disabling cognitive and/or motor dysfunction interfering with occupation or activities of daily living progressing over weeks to months, in the absence of a concurrent illness or condition other than HIV infection that could explain the findings. Method to rule out such concurrent illnesses and conditions must include cerebrospinal fluid examination and either brain imaging (computed tomography or magnetic resonance) or autopsy.

Slim Disease or HIV Wasting Syndrome

7021 HIV Wasting Syndrome, findings of profound involuntary weight loss $> 10\%$ of baseline body weight plus either chronic diarrhea (at least two loose stools per day for ≥ 30 days) or chronic weakness and documented fever (for ≥ 30 days, intermittent to constant) in the

absence of a concurrent illness or condition other than HIV infection that could explain the findings (eg, cancer, tuberculosis, cryptosporidiosis, or other specific enteritis).

7061 Recurrent pneumonia, acute onset within 12 months of most recent episode.

APPENDIX 3 DAIDS TOXICITY GRADES

Division of AIDS (DAIDS) Table for Grading the Severity of Adult and Pediatric Adverse Events

Version 2.0 - November 2014

<http://rsc.tech-res.com/safetyandpharmacovigilance/gradingtables.aspx>

APPENDIX 4 COCKCROFT-GAULT EQUATION TO CALCULATE SERUM CREATINE CLEARANCE

Online calculator:

<http://nephron.com/cgi-bin/CGSI.cgi>

Manual calculation:

Male:

Estimated Creatinine Clearance =
$$\frac{(140\text{-age in years}) \times \text{Body Weight (kg)}}{72 \times \text{Serum Creatinine (mg/dL)}}$$

Female:

Estimated Creatinine Clearance =
$$\frac{(140\text{-age in years}) \times \text{Body Weight (kg)} \times 0.85}{72 \times \text{Serum Creatinine (mg/dL)}}$$

1 pound = 0.4536 kilograms

APPENDIX 5 LABORATORY ASSESSMENTS

HEMATOLOGY		
WBC	Screening	Day 1, Week 4, Week 8, Week 12, Week 16, Week 24, Week 32, Week 40, Week 48, Week 60, Week 72, Week 84, Week 96, Early Term
RBC		
Hemoglobin		
Hematocrit		
Platelets		
Absolute Differential		
CHEMISTRY		
Glucose	Screening	Day 1, Week 4, Week 8, Week 12, Week 16, Week 24, Week 32, Week 40, Week 48, Week 60, Week 72, Week 84, Week 96, Early Term
Total Protein		
Albumin		
CK		
Total Bilirubin		
Direct Bilirubin		
Indirect Bilirubin		
AST		
ALT		
Alkaline Phosphatase		
LDH		
Amylase		
Lipase		
Electrolytes (Sodium, Potassium, Chloride, Bicarbonate)		
Calcium		
Phosphorous		
Creatinine + eGFR		
Uric Acid		
BUN		

LIPIDS		
Cholesterol	Screening	Day 1, Week 4, Week 12, Week 24
HDL		
LDL Calculated		
Triglycerides		
OTHER SERUM TESTS		
FSH	Screening	Optional; upon request
HCG	Optional; upon request	Optional; upon request
P1NP		Day 1, Week 12, Week 24, Early Term
CTX		Day 1, Week 12, Week 24, Early Term
URINE		
Urine Pregnancy test (if positive, request serum HCG)	Screening	Every 4 weeks (either done at in-clinic visits, or at home)
Urine Toxicology (drugs of abuse)	Screening	
Urine Creatinine		Day 1, Week 48, Week 96, Early Term
Urine Phosphorous		
β 2 microglobulin		
Macroscopic Urinalysis (no microscopic)	Screening	Day 1, Week 4, Week 8, Week 12, Week 16, Week 24, Week 32, Week 40, Week 48, Week 60, Week 72, Week 84, Week 96, Early Term
SEROLOGY		
HIV-1 RNA	Screening	Day 1, Week 4, Week 8, Week 12, Week 16, Week 24, Week 32, Week 40, Week 48, Week 60, Week 72, Week 84, Week 96, Early Term
HbSAg	Screening	Week 48, Week 96, Early Term
HCV Ab (if positive, reflex to HCV RNA)	Screening	Week 48, Week 96, Early Term

RESISTANCE		
Specimens for HIV Resistance testing at Monogram	Screening	Day 1, Week 4, Week 8, Week 12, Week 16, Week 24, Week 32, Week 40, Week 48, Week 60, Week 72, Week 84, Week 96, Early Term
Specimens for HIV Exploratory Resistance testing at BMS	Screening	Day 1, Week 4, Week 8, Week 12, Week 16, Week 24, Week 32, Week 40, Week 48, Week 60, Week 72, Week 84, Week 96, Early Term
PHARMACOKINETICS		
Intensive PK		Week 2 (optional)
Sparse PK		Week 4, Week 8, Week 12, Week 16, Week 24
IMMUNE PANEL		
%CD3+/CD4+	Screening	Day 1, Week 4, Week 8, Week 12, Week 16, Week 24, Week 32, Week 40, Week 48, Week 60, Week 72, Week 84, Week 96, Early Term
%CD3+/CD8+		
Absolute CD3/CD4		
Absolute CD3/CD8		
OTHER		
Pharmacodiagnostic (PDx)	Screening	
Plasma & Serum Back-ups	Screening	Day 1, Week 4, Week 8, Week 12, Week 16, Week 24, Week 32, Week 40, Week 48, Week 60, Week 72, Week 84, Week 96, Early Term

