ATV), (see [Section 1.1.1](#), Rationale to support study design). This risk mitigation is employed to decrease the probability of exposure to a subtherapeutic regimen and increase the probability of establishing clinical efficacy (number of responders at the Week 24) in treatment-experienced HIV-1 infected adults.

BMS expects BMS-955176 120 and 180 mg given with unboosted atazanavir to be generally safe and well-tolerated. Subjects in Arms 3 and 4 treated with unboosted ATV would potentially benefit from a more favorable lipid profile, fewer gastrointestinal (GI) side effects, and decreased indirect hyperbilirubinemia. In total, the potential clinical risks for subjects randomized to Arms 3 and 4 in Stage 2 do not outweigh the potential benefits of a Nucleoside- and Booster-sparing cART regimen that may offer both efficacy and long-term safety (including but not limited to improved bone mineral density, improved renal function, and improved lipid profile). Please see [Section 1.5](#) for further details on the overall risk/benefit assessment.

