3 INVESTIGATIONAL PLAN

3.1 Study Design and Duration

This is a randomized, active-controlled, staged, open-label clinical trial. Approximately 200 treatment-experienced HIV-1 subjects will be randomized to one of five treatment arms (approximately 40 per arm) in a staged fashion.

The data from the Week 24 analysis of Stage 1 and AI468038, including safety, efficacy and pharmacokinetics, will be examined to trigger the start of Stage 2 and confirm the two doses of BMS-955176 for study in Stage 2.

Stage 1:

In Stage 1, subjects will be randomly assigned 1:1 to one of two treatment arms and on Day 1 will begin dosing with:

- Arm 1 : BMS-955176 120 mg QD + ATV/r 300/100 mg QD + DTG 50 mg QD, or
- Arm 2: TDF 300 mg QD + ATV/r 300/100 mg QD + DTG 50 mg QD

Stage 2:

In Stage 2, subjects will be randomly assigned 1:1:1 to one of three treatment arms and on Day 1 will begin dosing with:

- Arm 3: BMS-955176 120 mg QD + ATV 400 mg QD + DTG 50 mg QD, or
- Arm 4: BMS-955176 180 mg QD + ATV 400 mg QD + DTG 50 mg QD, or
- Arm 5: TDF 300 mg QD + ATV/r 300/100 mg QD + DTG 50 mg QD

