3.1.3 Week 2 Intensive PK Visit

Subjects with anemia, defined as Hemoglobin < 11.0 g/dL, should be excluded from participation in the Week 2 Intensive PK Substudy.

Subjects in all arms will have the opportunity to participate in an elective Intensive PK Substudy visit at Week 2 (window for visit: Day 12-16). Approximately 60 subjects, 12 subjects from each arm, are expected to participate in the substudy; BMS may allow the substudy to over-enroll in an effort to have a sufficient number of complete datasets.

The series of 12 blood draws begins with pre-dose (0-hour) blood samples to be collected approximately 24 hours (20-28 hrs) after the morning doses of study drugs that were taken on the day before. Ten more samplings are drawn through the 12-hr time point, with one final sampling collected at the 24-hr time point, requiring the subject to either remain overnight in the clinic, or to return the next morning; the final 24-hr sample will be collected prior to administration of the morning doses of study drugs (See [Section 5.5.1](#)).

PK Tools/Job Aids will be provided to assist with the proper sequencing of dosing and blood sample collections, as well as the collection of required data.

3.1.4 Visits Week 4 - 96

Subjects are expected to be treated for the duration of 96 weeks. In each Stage, after Day 1 and the optional Intensive PK visit at Week 2, subjects will be required to attend 12 more in-clinic study visits over the 96-week treatment period, as follows:

- Visits are conducted every 4 weeks from Week 4 through Week 16
- Visits are conducted every 8 weeks from Week 24 through Week 48
- Visits are conducted every 12 weeks from Week 60 through Week 96

Visits should be scheduled as an interval from the Day 1/Randomization date, and within a window of 5 days earlier or later.

One of the visits Week 4 - 24 should meet the very specific timing requirements as outlined in [Section 5.5.2](#) for a pre-AM dose blood collection.

Telephonic visits will be conducted with each subject at visit Weeks 20, 28, 36, 44, 54, 66, 78, and 90 to conduct an adherence assessment and to continue retention efforts

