^b By definition, a pharmacodiagnostic sample (PDx) is a pre-treatment test to determine whether or not a patient is likely to respond to a drug (ie, a predictive test). Based on the results of clinical studies with BMS-955176, BMS may have to develop a PDx assay. Thus, PDx samples obtained at Screening in this study would be used for that sole purpose.

Table 5.1-2: Short-term Procedural Outline (AI468048)

Procedure	In-clinic Visit Day 1	In-Clinic Visit Optional Week 2 for Intensive PK (Day 12-16)	In-Clinic Visits Weeks 4, 8, 12, 16, 24, 32, 40, 48, 60, 72, 84, 96, and/or Early Termination (ET) (± 5 days)	Phone Visits Weeks 20, 28, 36, 44, 54, 66, 78, 90 (± 5 days)	Notes
Eligibility Assessments					
Inclusion/Exclusion Criteria	X				
Non-Laboratory Safety Assessments					
Full Physical Examination			WK 12, 24, 48, 96/ET		See Section 5.3.1 for requirements
Targeted Physical Examination	X		WK 4, 8, 16, 32, 40, 60, 72, 84		See Section 5.3.1 for requirements
Vital Signs & Physical Measurements	X		X		See Section 5.3.1 for requirements
Adherence Assessments			X	X	Including review of Dosing Diaries
Pre-treatment Events	X				See Table 5.1-1
Adverse Events Assessments	X	X	X		Serious and Non-serious AEs
Concomitant Medications	X	X	X		See Section 5.3.3
ECG	X		WK 4, 12, 24, 48, 96/ET		See Section 5.3.4 for requirements
Pregnancy Test	X	X	X		For females under age 55, an FSH level must be on record to confirm she is not a WOCBP if pregnancy testing is not being performed. If positive urine, request serum hCG quant. on lab requisition.

Table 5.1-2: Short-term Procedural Outline (AI468048)

Procedure	In-clinic Visit Day 1	In-Clinic Visit Optional Week 2 for Intensive PK (Day 12-16)	In-Clinic Visits Weeks 4, 8, 12, 16, 24, 32, 40, 48, 60, 72, 84, 96, and/or Early Termination (ET) (± 5 days)	Phone Visits Weeks 20, 28, 36, 44, 54, 66, 78, 90 (± 5 days)	Notes
Provide WOCBP with Home Pregnancy test kit(s) to be used during the in-clinic visit interval			WK 16, 24, 32, 40, 48, 60, 72, 84		Provide One Kit at Weeks 16 - 40 Provide Two Kits at Weeks 48 - 84 WOCBP subjects perform test Q4 weeks at home and report results to site.
Laboratory Assessments for Safety and Efficacy and Other Endpoints (See Appendix 5 for full details)					
Fasting Chemistry	X		X		Fasting overnight
Fasting Lipid Panel	X		WK 4, 12, 24, 48, 96/ET		Fasting overnight
Hematology	X		X		
Urinalysis	X		X		

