Fractional Excretion of Phosphorous (FePO4) (Urine creatinine and phosphorus, Serum creatinine and phosphorus)	X		WK 48 and 96/ET		
Plasma HIV-1 RNA	X	X	X		If collecting an HIV-1 RNA at an UNSCHEDULED visit, also collect samples for Resistance and Exploratory Resistance Testing
CD4 and CD8 T-cell counts	X		X		
HBV Surface Antigen			WK 48 and 96/ET		
HCV Serology			WK 48 and 96/ET		Positive HCV Ab will reflex to HCV RNA

Table 5.1-2: Short-term Procedural Outline (AI468048)

Procedure	In-clinic Visit Day 1	In-Clinic Visit Optional Week 2 for Intensive PK (Day 12-16)	In-Clinic Visits Weeks 4, 8, 12, 16, 24, 32, 40, 48, 60, 72, 84, 96, and/or Early Termination (ET) (± 5 days)	Phone Visits Weeks 20, 28, 36, 44, 54, 66, 78, 90 (± 5 days)	Notes
Resistance Testing (HIV-1 Drug Resistance)					
PhenoSense GT Plus Integrase	X		X		Samples stored and tested if needed (ie, analyses of subjects if deemed clinically relevant) See Section 5.4.2.2
PhenoSense Gag	X		X		
Next Generation Seq. - Qs Gag	X		X		
Exploratory Resistance (HIV-1 Drug Resistance)	X		X		Samples stored and tested retrospectively if needed (ie, exploratory analyses for subjects if deemed clinically relevant)
Intensive PK sample collection		X			Use of PK Tools for data collection recommended. See Section 5.5.1 for requirements
Sparse PK sample collection			WK 4, 8, 12, 16, 24		See Section 5.5.2 for requirements
Bone Biomarkers (PINP and CTX)	X		WK 12 and 24/ET		Serum collection
Renal Biomarkers (β2-microglobulin and creatinine)	X		WK 48 and 96/ET		Urine collection
Backup Serum and Plasma Sample	X		X		Samples stored and tested if needed
Outcomes Measures					
EQ-5D-3L Form	X		WK 12, 24, 32, 40, 48, 60, 72, 84, 96		Health Outcomes Questionnaire

Table 5.1-2: Short-term Procedural Outline (AI468048)

Procedure	In-clinic Visit Day 1	In-Clinic Visit Optional Week 2 for Intensive PK (Day 12-16)	In-Clinic Visits Weeks 4, 8, 12, 16, 24, 32, 40, 48, 60, 72, 84, 96, and/or Early Termination (ET) (± 5 days)	Phone Visits Weeks 20, 28, 36, 44, 54, 66, 78, 90 (± 5 days)	Notes
FAHI Form	X		WK 12, 24, 32, 40, 48, 60, 72, 84, 96		Functional Assessment of HIV Infection
Clinical Drug Supply					
Call IVRS to Randomize	X				
Dispense Study Drug	X		X		There is no dispensation at Week 96 or ET.

5.1.1 *Retesting During Screening or Lead-in Period*

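### Appendix 5 ends the fasting lipid panel at Week 24, while Table 5.1-2, which cites it for detail, runs the panel to Week 96 or early termination

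*Protocol*

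**What the plan says.** **Lipids.** In Table 5.1-2 (Section 5.1, Revised Protocol 03) the fasting lipid panel is marked at Day 1 and then at "WK 4, 12, 24, 48, 96/ET". The laboratory block in which that row sits is headed "Laboratory Assessments for Safety and Efficacy and Other Endpoints (See Appendix 5 for full details", so Appendix 5 is the cited source of detail. In Appendix 5 the lipid row lists Screening and then "Day 1, Week 4, Week 12, Week 24", with nothing later and no early termination sample. Neighbouring rows of the same appendix do name early termination: the bone markers, whose last planned visit is also Week 24, read "Day 1, Week 12, Week 24, Early Term", and chemistry runs through Week 96 and Early Term.

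**How lipids are used.** Section 1.1.3 gives the long-term safety case for Arms 3 and 4 as including "improved bone mineral density, improved renal function, and improved lipid profile". Section 5.6 names dyslipidemia as a toxicity of interest, contrasting Arms 3 and 4 with Arms 1, 2 and 5. Section 8.4.3 plans analyses of fasting lipids over time. On duration, Section 3.1.4 states: "Subjects are expected to be treated for the duration of 96 weeks".

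**Quality of life.** The EQ-5D-3L and FAHI rows of Table 5.1-2 list Day 1 and then "WK 12, 24, 32, 40, 48, 60, 72, 84, 96", without early termination. Section 3.5 requires an early termination visit of subjects who discontinue study drug, apart from those who withdraw consent to all procedures or lose the ability to consent freely.

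**The concern.** Two operational schedules in one protocol disagree on when a safety measurement is taken, and the one called the detailed list is the shorter. A site or laboratory working from Appendix 5 would stop drawing lipids a quarter of the way through treatment and take none from subjects who leave early. If different sites followed different lists, the later lipid data would be unevenly missing across sites. An analysis plan cannot recover samples that were never drawn.

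The questionnaire rows raise a lesser matter. A subject who stops early gives no form at the point of stopping. Several of the mandatory reasons for stopping in Section 3.5 (adverse events, virologic failure, emergent resistance) could plausibly be related to quality of life, so the missing form may be informative.

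**Working it through.** No error-rate or sample-size formula applies. The check sets the rows side by side and counts.

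**1. Lipid rows compared**

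| Time point | Table 5.1-2 | Appendix 5 |
|---|---|---|
| Day 1 | yes | yes |
| Week 4 | yes | yes |
| Week 12 | yes | yes |
| Week 24 | yes | yes |
| Week 48 | yes | no |
| Week 96 | yes | no |
| Early termination | yes | no |

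Three of the seven entries from Day 1 onward are missing from Appendix 5. Among planned post-baseline weeks it is two of five (48 and 96).

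**2. Share of treatment without lipids if Appendix 5 is followed.** (96 − 24) / 96 = 72 / 96 = 75%.

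**3. Number of panels.** Section 3.1 plans the following: "Approximately 200 treatment-experienced HIV-1 subjects will be randomized to one of five treatment arms (approximately 40 per arm) in a staged fashion".
- All five arms, everyone completing: 200 × 2 = 400 panels (Weeks 48 and 96).
- Stage 1 only, since the start of Stage 2 is conditional: 80 × 2 = 160.
- The table's last entry is Week 96 or early termination, so a subject who stops before Week 48 and attends that visit forgoes one panel instead of two. The protocol gives no dropout rate. Assuming 5% to 20% stop, all before Week 48, 10 to 40 of 200 subjects forgo one: 400 − 10 = 390 down to 400 − 40 = 360.

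**4. If Table 5.1-2 is followed.** The number of panels lost is zero.

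**5. Is this an accident of text extraction?** Unlikely. Revised Protocol 02 has the same mismatch between the same two tables, so it was carried through the amendment.

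**6. Quality-of-life forms.** There are nine post-baseline administrations. The intervals from Day 1 are 12, 12, 8, 8, 8, 12, 12, 12 and 12 weeks. A subject stopping after Week 12 therefore has earlier forms on file, the latest at most about 12 weeks old if visits are kept. A subject stopping before Week 12 has none after baseline. Under the same assumed 5% to 20%, 40 × 0.05 = 2 to 40 × 0.20 = 8 subjects per arm would lack a form at the point of stopping.

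**The case against.** The strongest reply is that Table 5.1-2 is the time and events schedule and does contain the later lipid visits. Section 5.2 says sites also receive a separate central laboratory manual, which is not available here, and no section says that sampling kits are built from Appendix 5. On that view the appendix row is a slip with no consequence. This stands as far as it goes: a reader might infer that the long-term lipid data are already lost, and the document does not support that. The loss is conditional. It does not remove the contradiction, because the table itself defers to the appendix and no rule of precedence is given. Back-up serum is stored, but no section assigns it to lipids.

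It is also fair that lipids are not a named primary, secondary or exploratory objective. They enter through the safety analyses, the rationale and the toxicity contrast.

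A reader might suppose that lipids are the only disagreement between the two tables. They are not: Table 5.1-2 marks HIV-1 RNA and the pregnancy test at the optional Week 2 visit, and Appendix 5 lists neither there.

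On quality of life, a reader might infer that the results would describe completers only. That is wrong, since early stoppers contribute every form up to their last scheduled visit. Nor is the missing entry a contradiction: no section says the forms are collected at early termination, another selected-visit row (sparse pharmacokinetics) also omits it, the objective is exploratory, and Section 8.4.6 leaves the analysis to the statistical analysis plan.

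**Conclusion.** The lipid inconsistency is real and should be corrected. Its size depends on which schedule is used. Under Appendix 5 there are no lipids for 75% of the treatment period and none at early termination, up to 400 panels at full enrolment with no dropout. The lipids-over-time analysis and the Arms 3 and 4 contrast would then stop at Week 24. Under Table 5.1-2 the loss is nil. The documents do not show which would be used, so the point is the ambiguity and not a demonstrated loss. The primary endpoint and the sample-size statement are unaffected, and the importance is minor to moderate.

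The absence of the questionnaires at early termination is a gap in the schedule for an exploratory objective. Closing it is an optional improvement; the per-arm count rests on an assumed dropout rate.

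**What to change.** Reconcile the two lipid schedules by adding Week 48, Week 96 and Early Term to the lipid row of Appendix 5, and check that the central laboratory manual agrees. The cost is a table edit and, if the manual follows the shorter list, a laboratory update. No extra visit or fast is needed, because fasting chemistry is already drawn at all three.

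Optionally, add early termination to the EQ-5D-3L and FAHI rows of Table 5.1-2. The cost is two short questionnaires at a visit that Section 3.5 already requires.
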